Gastric/Stool/Sputum/Sampling. Gastric sample of at least 1.0-2.0 mL will be collected weekly by the research coordinator, immediately following insertion of a new feeding tube, by gently aspirating gastric contents from the feeding tube into a syringe. Gastric aspiration assessment for feeding tube placement as per NICU protocol. One baseline pH will be obtained at start of study. To assess gastric pH, the research coordinator will use one-two drops of the gastric sample to test using Hydrion pH strips and Fischer Scientific Horiba LAQUA twin pH 11 meter. The rest of the gastric sample will be used to analyze the microbiome and level of inflammatory markers. Stool samples will be collected weekly by the research nurse and pH check of sample will be done. Following collection, all samples will be placed in a sterile specimen container and immediately frozen at -80 degrees Celsius for later analysis. This team has extensive experience in the collection of gastric aspirates, and stool from premature VLBW infants in the NICU as well as the analysis of inflammatory markers and 16S rRNA sequencing of these samples. Oropharyngeal swabs will be collected weekly by the research coordinator (a registered nurse experienced in the care of critically ill infants) by placing a tiny soft brush into the infant's mouth and gently rotating the swab to collect the infant's saliva.

Microbiota Sequencing and Analyses: DNA from samples will be extracted and analyzed as described above (see Aim 1).

Inflammatory Response. The samples will be analyzed for inflammatory markers using a combination of multiplex technologies using the BioRad Bio-Plex platform as well as S100A12 and calprotectin immunoassays.

Statistical Analysis

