Data integrity will be evaluated using descriptive statistics (e.g.: means, standard deviations, frequencies, percents, range) appropriate for measurement level. Checks for implausible or outof-range values, distributional forms, the presence and distribution of censored values (e.g.: inflammatory markers), and missingness will be performed. Data transformations (e.g.: Box-Cox family of transforms) will be made, if required, based on evaluation of model fit and tenability of assumptions. If applicable, regression techniques which can accommodate censored variables (e.g. MPLUS version 8 or higher)⁵⁸ will be employed. Selected variables (e.g.: type of feed (mother's breast milk or donor breast milk), whether NPO, antibiotic use, gestational age, chronological age, gastric pH and sex) will be screened for potential inclusion as covariates in each of the statistical models tested. Associations between each potential covariate and the respective dependent variable will be examined, and only those variables having a p<.10 association and whose inclusion improves model fit will be retained. The general modeling strategy will be a generalized linear mixed model (GLMM) approach. A GLMM is able to accommodate different numbers of measurements between subjects, utilize data from subjects when some of the data is missing (that is, subjects with some missing data points will not be dropped from analysis), can incorporate time-varying covariates, flexible covariance structures, and a variety of dependent variable distributions (including dichotomous), and thus will be able to accommodate the analyses proposed. Model fit and strength of association will be evaluated using Vonesh's GOF macro for SAS. Our primary goal will be to assess differences in marginal least squares means between the dwell time groups. All analyses will be performed using SAS software version 9.4 or later. Statistically significant interaction effects will be evaluated using simple main effects analyses via the SLICE option available in the SAS/STAT GLMM procedures. Due to the number of inferential tests planned, it is not practical to maintain a 5% experiment-wise Type I error rate; however, significance levels will be adjusted to maintain a model-wise 5% Type I error rate through use of a Benjamini-Hochberg approach.

Data Entry and Management

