A code key stored separate from the data set will be used. The code key will be kept in a locked cabinet in the research office. All data will be entered into a REDCAP database having integrated data quality and consistency checks. The study database created in REDCap will be password-protected and housed on a designated database server. Data quality will be monitored and assured as reported and as entered into the database. All hardcopy forms will be

Variable	Measurement	Timing
Descriptive (1-2) below		
1. Maternal, prenatal and perinatal demographics	Maternal history, prenatal and perinatal complications and medications, mode of delivery, antibiotic use, steroid use	Collected upon entry into study.
2. Infant demographics	Race/ethnicity, sex, gestational age, birth weight, Apgar scores, resuscitation at birth and neonatal acuity (SNAP II) score, type of feeding, whether or not the infant is NPO, medications effecting gastric pH, chronologic age, NPO, number of days and type of antibiotics	Collected upon entry into study and during the 4 week study period. Antibiotic data tracked for 6 weeks
Microbial analysis of feeding tubes, feeding tube hubs and residual intraluminal liquid Analysis of gastric contents (1-2)	Culture based analysis and microbial analysis (16S rRNA and metagenomics sequencing). Presence of biofilm in feeding tube or Replogle tube	Following removal of each feeding tube for 4 weeks
below		
1. Microbial analysis	16S rRNA and metagenomics sequencing	Weekly for 4 weeks
2. Inflammatory markers	Analysis of inflammatory markers	Weekly for 4 weeks
3. pH testing	Measuring acidity	Initially and weekly for 4 weeks
Analysis of stool (1-2) below		
1. Microbial analysis	16S rRNA and metagenomics sequencing	Weekly for 4 weeks
2. Inflammatory markers	Analysis of inflammatory markers	Weekly for 4 weeks
3. pH testing	Measuring acidity	Weekly for 4 weeks
Nutritional outcomes (1-6) below		
1. Enteral intake	24-hour enteral feeding intake in mL/kg	Daily for 6 weeks
2. Time to full feeds	First day infant received ≥120 mL/kg/d of enteral feedings. First day infant received 150ml/kg/d	Recorded daily until 150 mL/kg/d reached (up to 6 weeks)
3. Hours of PN	Number of hours infant received some parenteral nutrition	Daily for up to 20 weeks

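### The covariate screen allows weekly, post-randomisation gastric pH into the primary tube-culture model, where it could alter the dwell-group difference in marginal means

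*Combined protocol and SAP*

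**What the plan says.** The Statistical Analysis section names feed type, NPO status, antibiotic use, gestational and chronological age, "gastric pH and sex) will be screened for potential inclusion as covariates in each of the statistical models tested". Retention has two conditions: "only those variables having a p<.10 association and whose inclusion improves model fit will be retained". The mixed model is chosen partly because it "can incorporate time-varying covariates", and the section states: "Our primary goal will be to assess differences in marginal least squares means between the dwell time groups". The Sample Size section confirms that the primary-aim model takes selected covariates.

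On timing, the sampling section says "One baseline pH will be obtained at start of study". It adds that gastric samples "will be collected weekly by the research coordinator, immediately following insertion of a new feeding tube". The data-collection table times gastric pH testing as "Initially and weekly for 4 weeks", and its Covariates rows list gastric pH as weekly. Medications that affect pH are recorded over the four study weeks.

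No text says whether the baseline or the weekly pH enters a model, or which tube a weekly reading is paired with. No text bars post-randomisation covariates from the primary model or commits to an unadjusted primary analysis.

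**The concern.** Randomisation protects the comparison of dwell groups as long as the model adjusts only for things that dwell assignment cannot have changed. Weekly pH is read while infants are on their assigned schedule, so it lacks that protection. If a reading is paired with the tube just removed, it also comes after the outcome, because the aspirate is drawn through the replacement tube. The trial's own rationale runs from contaminated tube to stomach, so an effect on pH is conceivable, although it is nowhere asserted.

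The retention rule is no safeguard: a variable that follows from the outcome tends both to be associated with it and to improve fit. What is at stake is the marginal dwell-group difference. A secondary matter is that a standard mixed model omits rows with a missing covariate, so a cultured tube without a matching pH would drop out. The assurance that "subjects with some missing data points will not be dropped from analysis" concerns infants, not such rows.

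**Working it through.** **Inputs from the documents.** Five tube sections, five colony types and four weeks; a difference to detect of 3.0 ln CFU; 134 infants enrolled with a 10% loss. The plan's count reproduces: 5 × 5 = 25 rows per infant-week, and 25 × 4 = 100 per infant. The stated power limit of .97 cannot be reproduced, because the pilot means and covariance matrix are not given.

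**Assumed.** The pH–load correlation, any effect of dwell on pH, and the share of infant-weeks without pH. None is in the documents.

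**1. pH follows the load in the removed tube.** Let r be the within-group correlation and D the true difference. The groups then differ in pH by r × (SD of pH / SD of load) × D. The within-group slope of load on pH is r × (SD of load / SD of pH). Subtracting their product gives an adjusted difference of D × (1 − r²), with independent weeks. The simulation used 60 infants per arm, 4 weeks, infant SD 2, residual SD 3 and 200 runs per setting.

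| Assumed r | 3.0 × (1 − r²) | Shrinkage | Simulated, unadjusted → adjusted | pH passes p<.10 |
|---|---|---|---|---|
| 0.1 | 2.97 | 1% | 2.98 → 2.95 | 67% |
| 0.2 | 2.88 | 4% | 3.00 → 2.89 | 99.5% |
| 0.3 | 2.73 | 9% | 3.01 → 2.77 | 100% |
| 0.5 | 2.25 | 25% | 2.98 → 2.33 | 100% |

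The simulated shrinkage is slightly smaller at the higher correlations because weeks within an infant are correlated. The effect here is attenuation only: if D = 0, the adjusted value is also 0.

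**2. Dwell shifts pH, and pH then affects load** (for example, if a reading is paired with the next tube). If pH is higher by d in the 7-day group and load rises by b ln units per pH unit, the adjusted difference is 3.0 − b × d. With b = 1 and d = 0.25, 0.5 or 1, this gives 2.75, 2.5 or 2.0 (simulated 2.74, 2.47 and 2.03). If d has the opposite sign, the difference grows: d = −0.5 gives 3.5. The direction is therefore not fixed.

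**3. Dwell does not affect pH.** With d = 0 there is no bias. If pH also predicts load, adjustment gains precision: SE ratios of 0.990, 0.977 and 0.924 at r of 0.2, 0.3 and 0.5, about 1%, 2% and 8% smaller.

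**4. The interaction.** Weekly pH is one value shared by all 25 rows of an infant-week, so an additive term cannot separate colony types. In a balanced fit with infant and infant-week effects, the interaction coefficient was 2.9816 (SE 0.1732) both with and without pH. Under an assumed unstructured covariance it moved by about 1% or less.

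**5. Missing pH.** 134 × 0.9 = 120.6, taken as 120 infants, 480 infant-weeks and 12,000 rows. Losing 5%, 10% or 20% of weeks removes 600, 1,200 or 2,400 rows.
- With NPO status in the model and a constant dwell effect, the simulation showed no bias (3.05 with and without the lost rows at 20%). The SE of the marginal difference rose by 1%, 3% or 6%.
- For the interaction, 1/√(1 − f) gives 1.026, 1.054 and 1.118 if weeks are independent within infant and colony type.
- If an infant-by-colony variance equal to a quarter of the weekly residual variance persists across weeks, and loss is spread evenly over infants, √[(0.25 + 0.25/(1 − f))/0.5] gives 1.013, 1.027 and 1.061.

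**The case against.** The strongest reply is that the harm is conditional at every step. The plan does not say that the weekly value will be used. It does not pair a reading with the tube just removed: the same aspirate describes the stomach at the start of the next tube's dwell. It does not say that dwell or contamination changes pH; Aim 2 names dysbiosis and inflammation, not pH. The size of any bias is wholly assumed, and at r of 0.1 to 0.2 it is only a few per cent. The interaction that the power analysis calls primary is hardly touched. pH testing needs only a drop or two of sample, so missing readings may be rare.

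All of this stands and limits the point. It does not remove it, because under either pairing a weekly reading is post-randomisation and the rule as written admits it.

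It is also fair to object that singling out pH would be inconsistent. On-study NPO status and antibiotic use are in the same list. Aim 3 makes necrotising enterocolitis and late-onset sepsis outcomes of dwell group, and presumed sepsis is defined partly by antibiotic treatment. pH-altering medications are likewise recorded during the study weeks. Even the baseline pH is not shown to precede randomisation, since no randomisation time is given. This part is correct, and the fix should cover all of these variables.

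A reader might infer that the primary analysis will adjust for a consequence of its own outcome, or that the power for the interaction is undermined. The documents support neither: the first needs an unstated pairing and an unstated causal link, and the second conflicts with step 4.

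**Conclusion.** The point holds in a limited form and is worth considering rather than critical. As written, the screening rule can put a post-randomisation variable into the primary dwell comparison, and its two retention conditions do not guard against this. For the marginal difference, the consequence ranges from none (dwell does not affect pH) to a shrinkage of 1%, 4%, 9% or 25% at assumed r of 0.1, 0.2, 0.3 or 0.5 with independent weeks, if pH follows tube load. If dwell shifts pH by another route, the change could go either way. The interaction is essentially unaffected by an additive term; exact equality needs the balanced random-intercept structure. Infant-weeks without pH would cost a modest amount of precision that the documents do not allow one to quantify. A reader might infer that these lost rows also bias the result. That would need a dwell effect that differs in the weeks without pH, and nothing in the documents points to one.

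**What to change.** Add to the Statistical Analysis section:

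> In the primary tube-culture model, only values recorded before randomisation (for example gestational age, sex, baseline gastric pH) may be screened as covariates. Weekly gastric pH, and on-study use of pH-altering medications, NPO status and antibiotic use, will not be candidates in the primary model; they may be added in a sensitivity analysis fitted with and without them on the same rows.

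Fitting both models on the same rows separates the effect of adjustment from the effect of lost rows. The first sentence also bars feed type as recorded during the study.

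The change takes two sentences and no new data. Its cost is any precision these variables would have added to the marginal comparison. For weekly pH that is an SE about 1% to 8% smaller at assumed r of 0.2 to 0.5, and it is a clean gain only if dwell does not affect pH. For the interaction, essentially nothing is lost by leaving out weekly pH.

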As per standard NICU protocol, all infants will begin receiving TPN within 24 hours of life. In addition, all infants will have an orogastric (OG) or nasogastric (NG) tube placed upon admission to the NICU and begin receiving some enteral feeding within 72 hours. Length of insertion of the OG/NG tube is determined by measuring from the tip of the nose to the tip of the ear lobe and then halfway between the xyphoid process and umbilicus (Ellett et al., 2011). Minimum insertion length based on the weight of the infant (Cordero et al., 2011). If the infant receives an X-ray upon admission, placement of the OG/NG tube is verified. Placement is also verified if additional X-rays are taken during the study as per usual OG/NG placement protocol in the NICU. Depending on the infant's gestational age, weight, and clinical status, feedings are initiated at up to 20mL/kg/d and advanced daily by no more than 20mL/kg/d toward a goal of 120-150mL/kg/d divided into 8 equal feedings per day using the established University of Florida Children's Hospital NICU feeding guidelines. If mothers own breast milk is unavailable, infants will be provided donor breast milk as per NICU standard care.

Consent Process

Within 72 hours of life, and within 24 hour of initiating feeds of \leq 20 mL/kg/d, informed consent will be obtained from the mother either in her hospital room or the NICU. The PI or research coordinator will ask the mother's or infant's nurse whether the mother is willing to speak with someone regarding enrolling her infant in a research study. If the mother says yes, the PI or research coordinator will explain the study and invite the mother to have her infant enrolled. All questions will be answered and mothers will be provided ample time to discuss with family and friends. If the mother consents and is providing breast milk to her infant, she will also be consented since will be providing 2 samples of breast milk for analysis

Breast Milk Feedings

Current practice in this NICU is to provide donor breast milk to all infants born prior to 30 weeks until they are 32 weeks post conceptual age. For this study, all infants will receive either mother's own breast milk or donor human milk for the 4 week study. If the infant is scheduled to be discharged prior to 4 weeks, the infant will be transitioned to formula as per NICU standards.

Procedure

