1.PNALD	Liver function tests (level of direct bilirubin, alkaline phosphatase, AST and ALT)	Weekly or biweekly for 6 weeks Peak alkaline phosphatase and Peak direct bilirubin for up to 20 weeks or discharge
2. Hours of central venous line access	Number of hours infant has a central venous line	Daily for up to 20 weeks
3. Growth indices	Weight, length, and head circumference	Daily for 4 weeks and at discharge
4. Episodes of late onset sepsis	Episodes of culture proven or presumed sepsis (treated with \geq 3 days of antibiotics but with negative cultures)	Daily from birth up to 20 weeks
5.Episodes of NEC	Episodes of radiologic or surgical evidence of NEC	All incidences for up to 20 weeks
6. Length of hospital stay	Days infant remains in hospital	From birth until discharge
Covariates (1-5) below		
1. Gastric pH	pH of gastric aspirates, use of medications which affect gastric pH	Gastric pH analysis will be done weekly, information regarding medications will be collected during the 4 weeks study period
2. Oropharyngeal swabs	Time of last feed, oral medications	Sputum samples weekly for 4 weeks
3.Analysis of maternal breast milk or donor milk	Microbiota and metagenomic sequencing	At week 1 and week 4

4. Nutritional data	Medications and disease processes associated with decreased intestinal motility, episodes and duration of kangaroo care	Upon entry into study and for 4 active weeks.

visually inspected before data entry. A manual comparison of randomly selected data hardcopy forms with data output listing generated from the study database will be performed, and consistency checks will be generated by SQL or SAS programs as part of data cleaning procedures. The system will assign a global unique identifier to each enrolled subject that will serve as the subject id. Study case report forms (CRFs) will be maintained in study specific folders and when CRFs not actively being processed, will be secured in locked file cabinets. In addition to the use of passwords and other security measures, all documents containing identifying information are considered confidential materials and will be safeguarded. Data to be collected are found in Table 3. Data collected in REDCap will be shared with an outside affiliated researcher at Old Dominion University for secondary data analysis. All data sets shared will be verified with CTSI REDCap, before giving outside researcher access.

7. Possible Discomforts and Risks:

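### The covariate screen allows on-study NPO status into the Aim 3 models of enteral intake and time to full feeds, where it is partly the outcome itself

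*Combined protocol and SAP*

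**What the plan says.** The Statistical Analysis section gives an open list of candidate covariates. After type of feed, it names "whether NPO, antibiotic use, gestational age, chronological age, gastric pH and sex) will be screened for potential inclusion as covariates", and it applies the screen to each model tested. The retention rule is that "only those variables having a p<.10 association and whose inclusion improves model fit will be retained". The association meant is with that model's own dependent variable. Among the stated merits of the GLMM is that it "can incorporate time-varying covariates, flexible covariance structures".

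The variable table under Data Entry and Management lists NPO status and days and type of antibiotics under infant demographics, with the timing "Collected upon entry into study and during the 4 week study period" (antibiotics for 6 weeks). The same table defines enteral intake as "24-hour enteral feeding intake in mL/kg" and time to full feeds as "First day infant received ≥120 mL/kg/d of enteral feedings", with a second threshold at 150 mL/kg/d. Presumed late onset sepsis is defined there by antibiotic treatment of at least "3 days of antibiotics but with negative cultures".

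Under Standard Infant Feeding Protocol, "feedings are initiated at up to 20mL/kg/d and advanced daily by no more than 20mL/kg/d toward a goal of 120-150mL/kg/d". Aim 3 hypothesises better nutritional outcomes in Group 1. No section fixes a covariate set, names an unadjusted main analysis, or exempts the nutritional models from the screen. The power section speaks only of selected covariates.

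**The concern.** A covariate measured after randomisation can carry part of the treatment effect. Adjusting for it changes the question from what assignment to 48 hours does to what it does with that covariate held equal.

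NPO is the clearest case because of how the two outcomes are defined. A full NPO day has an enteral intake of zero, and NPO days during the climb can postpone the first day at 120 or 150 mL/kg/d. A screen on association with the outcome will therefore tend to pick NPO. The Background section says contaminated tubes raise the risk of feeding intolerance, necrotizing enterocolitis and sepsis. That these lead to NPO days is my inference. If it is right, one route by which shorter dwell time could improve nutrition is removed from the estimate, and a real benefit could be reported as smaller or absent. The plan's stated target, least squares means by group, does not avoid this, because those means compare the groups at common covariate values.

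**Working it through.** The plan gives no figure to reproduce here, and the documents give no NPO rates. The earliest-day arithmetic uses the plan's own limits; the rest is illustration.

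**Earliest day of full feeds.** Starting at 20 and rising by 20 mL/kg/d each day, volume on feeding day d is at most 20d. Then 120/20 = 6, so day 6; 150/20 = 7.5, so day 8. At these maximum rates each full NPO day in the climb adds at least one day.

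**A. Daily intake with a day-level NPO flag.** Assumed: fed-day intake F of 80-120 mL/kg, zero on NPO days, NPO on 10% of days in Group 1 and 15-20% in Group 2.
- No group difference on fed days: unadjusted difference = F × (p2 − p1), from 80 × 0.05 = 4 to 120 × 0.10 = 12 mL/kg/d. Adjusted for the flag it is 0, because intake is the same in both groups within each NPO stratum.
- A further 5 mL/kg/d on fed days in Group 1: unadjusted adds 0.9 × 5 = 4.5, giving 8.5 to 16.5. The adjusted estimate averages 5 (fed days) and 0 (NPO days) with stratum weights ab/(a+b), where a and b are the two groups' shares of days in that stratum. For 10% v 15%: weights 0.9 × 0.85/1.75 = 0.437 and 0.1 × 0.15/0.25 = 0.060, so 5 × 0.437/0.497 = 4.4. For 10% v 20%: 0.424 and 0.067, so 4.3.

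**B. Time to 120 mL/kg/d.** Assumed throughout: 60 per arm (134 less 10% is about 120, split equally), two-sided 5%, true total difference 2.0 days. Day = 6 + NPO days + other delay (gamma, mean 6, SD 3) + any direct effect. NPO days come in Poisson episodes of 1 + Poisson(1) days, with mean 1 or 2 in Group 1 plus the stated shift in Group 2. All NPO days fall before full feeds and each costs one day. NPO is retained if it passes p<.10 and improves AIC; AIC is a stand-in, since the plan names a goodness-of-fit macro but no criterion. Retention was 98-100%.

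| NPO shift (days) | Unadjusted power (estimate 2.0) | Yes/no NPO: estimate; power | Count of NPO days: estimate; power |
|---|---|---|---|
| 0 | 82-90% | 2.0; 88-93% | 2.0; 95% |
| 0.5 | 81-88% | 1.6-1.7; about 77% | 1.5; 77% |
| 1.0 | 79-86% | 1.3-1.5; 56-62% | 1.0; 42-43% |
| 2.0 | 76-84% | 0.8-1.2; 21-36% | 0; 5% |

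The yes/no column comes first because the plan names NPO as a status, not as a count of days.

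**C. Late onset sepsis and antibiotics.** Assumed: sepsis 20% v 40%, antibiotics in 90-100% of septic and 30-50% of other infants, antibiotic use depending only on sepsis, 60 per arm. The odds ratio is (0.2/0.8)/(0.4/0.6) = 0.375 with or without adjustment. Power falls from 67-69% to 46-57%. Type I error is 5-6% both ways.

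**The case against.** The strongest reply is that the defect is conditional. The plan says variables are screened for potential inclusion and nowhere says that on-study NPO will enter a nutritional model. Bias also needs dwell time to change NPO, which the documents do not state; without it, adjustment is harmless and raises power. Both points stand, and they set the claim at what the text permits. The text still does not exclude on-study NPO, and a baseline-only reading is strained: the data are collected on study, time-varying covariates are advertised, and consent is tied to the start of feeds, so NPO at entry may vary little.

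Second, illustration B is not derived from the plan. The feeding protocol caps the daily advance but sets no minimum. An infant averaging 10 mL/kg/d who resumes at the earlier volume and catches up within the cap could reach 120 on day 12 with or without one NPO day. NPO after full feeds cannot delay them. Equal allocation is assumed, and Sample and Setting gives N = 151, not 134; at 75 per arm the one-day-shift power is about 88-93% unadjusted and 53% adjusted for NPO days. The planned Benjamini-Hochberg adjustment is not modelled. All of this stands, so B shows direction and plausible scale only.

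Third, a reader might infer from the count-of-days column that adjustment would abolish the effect. With the yes/no status the plan names, illustration B shows attenuation, not abolition. A reader might also infer a biased sepsis odds ratio. Illustration C shows lost power only.

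**Conclusion.** The concern holds in limited form. The screen permits on-study NPO in the models of enteral intake and time to full feeds, and its retention rule favours a variable that is partly the outcome. If dwell time affects NPO, the adjusted difference omits that part of the effect and understates a nutritional benefit. The documents do not fix the size. Under B's assumptions, a true 2.0 days becomes roughly 0.8 to 1.7 days with a yes/no covariate as the NPO shift goes from 2 days to 0.5. If dwell time does not affect NPO, there is no bias.

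For late onset sepsis, antibiotics are part of the presumed-sepsis definition, so adjusting for on-study use can cost power; no bias is claimed.

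A reader might extend the point to the primary aim. The documents do not support that: the powered quantity is the Dwell Group by Colony Type interaction, NPO is not a component of bacterial counts, and nothing here shows bias in the contamination models. The point should be fixed because the remedy is cheap and, without it, a null nutritional result could not be told apart from one produced by adjustment.

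**What to change.** Add to the Statistical Analysis section that the main dwell-group comparison for enteral intake and time to full feeds will not adjust for on-study NPO, and that for late onset sepsis will not adjust for on-study antibiotic use. In these models use only values recorded before randomisation, with baseline covariates already collected (for example gestational age, birth weight and sex), and state when randomisation falls relative to the entry data. Models with on-study NPO or antibiotics can be kept as labelled exploratory or mediation analyses.

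The cost is wording; no new data are needed. The downside is some lost precision if dwell time does not affect NPO: about 82-90% power instead of 88-95% in illustration B. Replacing the screen in the contamination models is optional and not part of this point.
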